8.1.2.11. Behavior Problems Inventory—Short Form (BPI-SF)

The Behavior Problems Inventory (BPI-SF) will be completed at Baseline (Visit 3) and at the End of Treatment (Week 13, Visit 16). The BPI-SF is a caregiver-completed rating scale for assessing self-injury, aggressive and stereotyped behavior. Each item is measured for frequency and for severity for the self-injurious behavior and aggressive/destructive behavior subscales. The frequency is scored on a 5-point scale, where 0=never; 1=monthly, 2=weekly, 3=daily, 4=hourly. The severity is scored on a 3-point scale, where 1=mild, 2=moderate, 3=severe. The items are grouped in three subscales: Self-Injurious Behavior (score ranges from 0 – 32 for frequency and 8 – 24 for severity), Aggressive/Destructive Behavior (score ranges from 0 – 40 for frequency and

10-30 for severity), and Stereotyped Behavior (score ranges from 0-48 for frequency). The score for each domain is the sum of the items within that domain. The total frequency score is the sum of the frequency score for the three domains The total severity score is the sum of the severity scores for aggressive/destructive behavior and self-injurious behavior. Missing items will be imputed as defined in section 4.2.3. A domain score will only be calculated if all items in that domain are answered or can be imputed. Lower scores indicate lesser frequency and severity in behavior problems. Within subject change is the difference between the score at EOT and the score at Baseline (Visit 3).

Summary statistics for the total and domain scores and their changes from baseline in the frequency and severity of the domain-specific BPI-SF scores will be displayed at End of Treatment. Within subject changes will be analyzed using a Wilcoxon signed rank test. The frequency and severity scores will be presented in waterfall plots, histograms, and violin plots, and the domain scores will be presented in a forest plot, as described in Section 8.1.2.

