9.5.9.9 Behavior Problems Inventory-Short form (BPI-SF)

The Behavior Problems Inventory (BPI-SF) will be completed at Baseline (Visit 3) and at the EOT (Week 13, Visit 16). The BPI-SF is a caregiver-completed rating scale for assessing self-injury, aggressive and stereotyped behavior.⁵⁹ Frequency is assessed for all three types of behavior on a five-point scale: 0 (Never), 1 (Monthly), 2 (Weekly), 3 (Daily), and 4 (Hourly). For self-injury and aggression, severity is also assessed on a 3-point scale of mild, moderate, or severe.

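### The SAP gives no BPI-SF severity value for a behaviour rated as never occurring, and its printed severity minimums of 8 and 10 leave no room for one

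*SAP*

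**What the plan says.** SAP 8.1.2.11 defines two ratings. On scope: "Each item is measured for frequency and for severity for the self-injurious behavior and aggressive/destructive behavior subscales". On frequency: "The frequency is scored on a 5-point scale, where 0=never; 1=monthly, 2=weekly, 3=daily, 4=hourly". On severity: "The severity is scored on a 3-point scale, where 1=mild, 2=moderate, 3=severe". Protocol 9.5.9.9 agrees and adds no further level: "For self-injury and aggression, severity is also assessed on a 3-point scale of mild, moderate, or severe".

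Domain scores are item sums. The SAP prints a severity range of 8 to 24 for self-injurious behaviour, and for aggressive/destructive behaviour "10-30 for severity". It continues: "The total severity score is the sum of the severity scores for aggressive/destructive behavior and self-injurious behavior". On completeness: "A domain score will only be calculated if all items in that domain are answered or can be imputed".

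Three other provisions bear on the point:

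- SAP 4.2.2 does not impute missing baseline values.
- SAP 4.2.3 carries the last item response forward after baseline when three or fewer items are missing. It does not say whether that count is per domain or per assessment.
- The BPI-SF is completed only at Visit 3 and Visit 16, so the only value that can be carried forward to Visit 16 is the baseline one.

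**The concern.** A behaviour that does not occur has a frequency code but no severity code. The text allows three readings:

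1. **Entered as 1.** An absent behaviour scores the same as a mild one, and a mild behaviour that stops shows no improvement. This conflicts with the section's own statement that lower scores mean less severe problems.
2. **Left blank and treated as missing.** One absent behaviour at baseline removes that domain's severity score and the total. At Visit 16, a behaviour that has stopped either gets its old severity back by carry-forward or leaves the child without a score.
3. **Counted as answered and scored 0.** The scores then behave as intended, but the printed minimums of 8 and 10 are wrong.

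Severity domain and total scores are summarised, plotted and tested with the Wilcoxon signed rank test. Under readings 1 and 2, severity can disagree with frequency for scoring reasons alone. Reading 2 also changes how many children are analysed. Two programmers following this section could produce different results.

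**Working it through.** **Inputs.** From SAP 8.1.2.11: frequency codes 0–4, severity codes 1–3, frequency maxima 32 and 40, severity ranges 8–24 and 10–30. From SAP 4.2.2 and 4.2.3: the missing-data rules described above.

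**Step 1: reproduce the printed ranges.** Number of items = maximum score ÷ highest code.

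- Self-injury: 32/4 = 8 and 24/3 = 8.
- Aggression: 40/4 = 10 and 30/3 = 10.
- Severity minimums: 8 × 1 = 8 and 10 × 1 = 10.

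The printed ranges are reproduced exactly, and they hold only if every item carries a severity of at least 1. The implied total is 8 + 10 = 18 to 24 + 30 = 54.

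**Step 2: change for one behaviour that stops, from baseline severity s.**

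- Reading 1: 1 − s
- Reading 2, when carried forward: s − s = 0
- Reading 3: 0 − s = −s

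**Step 3: worked cases.** These are constructed response patterns and assume no prevalence. In every case except the fourth, all items concerned are rated at baseline, so that reading 2 has a baseline score.

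| Case | Reading 1 | Reading 2 | Reading 3 |
|---|---|---|---|
| Eight mild, hourly self-injury behaviours all stop | 8 × (1 − 1) = 0 | 8 blanks, more than 3: no score | 8 × (−1) = −8 |
| Three severe self-injury behaviours stop, five unchanged | 3 × (1 − 3) = −6 | 0, if these are the only blanks counted | 3 × (−3) = −9 |
| Eight moderate self-injury behaviours, three stop | 16 to 13 = −3 | 16 to 16 = 0 | 16 to 10 = −6 |
| Two mild self-injury behaviours, six never at baseline, both stop | 8 to 8 = 0 | no baseline score | 2 to 0 = −2 |
| Two moderate behaviours stop in each domain, all 18 rated at baseline (total severity) | 4 × (1 − 2) = −4 | 0 if the limit is per domain (2 and 2 blanks); no score if per assessment (4 blanks) | 4 × (−2) = −8 |

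In the first case the frequency score moves by 8 × (0 − 4) = −32, its full range.

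**Step 4: floor under reading 1.** A child with none of the 18 behaviours scores 18 of 54, which is 18/54 = 33% of the maximum. The largest possible fall in the total is 54 − 18 = 36, against 54 − 0 = 54 under reading 3.

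**The case against.** The strongest reply is that what is shown is an unstated rule, not a wrong score. The CRF coding and the instrument's scoring rules are not in the documents and may already decide the matter.

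Nor are the readings equally supported. Taken literally, only reading 1 gives every child a score inside the printed ranges. Reading 2 is the weakest, because an item rated never has been answered on frequency and its inapplicable severity need not count as missing. Under reading 3 the fault shrinks to misprinted minimums. That is plausible, since SAP 8.1.2.13 prints 9–36 for GIHQ Medications frequency on a nine-item scale whose codes start at 0. The worked cases were also chosen to separate the readings, and the frequency scores and ABC-2 cover much of the same ground.

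Most of this stands as a limit on reach. It does not remove the defect:

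- If the CRF enters 1, absent is indistinguishable from mild.
- If it leaves a blank, nothing in the SAP keeps that blank out of the missing-item rules.
- If it enters 0, the printed minimums are wrong.

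The section needs correcting in each case. The SAP writes down comparable rules elsewhere, for example scoring a not-applicable response as 0 in the Autism Mental Status Exam (SAP 5.3).

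**Conclusion.** The concern holds. The severity value for an absent behaviour is undefined in both documents, and on every reading either a stated rule or a printed figure is wrong. The same clinical change can score −6, 0 or −9, or 0, no score or −8, depending only on the coding chosen.

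The result rests on the printed coding and ranges alone. How many children would lose a score under reading 2 cannot be estimated without item prevalence; it could be anywhere from 0 to all 20.

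The reach is limited. The BPI-SF is one of 17 secondary efficacy variables in SAP 7.1, there is no primary efficacy endpoint, significance levels are nominal (SAP 7.5), and the BPI-SF frequency scores still record a behaviour that stops. The correction should be made, but the point does not threaten the study's main conclusions.

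**What to change.** First check the CRF coding and the instrument's scoring rules, before database lock. Subject to that check, add to SAP 8.1.2.11:

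*Item severity is set to 0 whenever that item's frequency is 0, before any missing-data rule is applied. A blank severity is missing only when that item's frequency is above 0 or is itself missing.*

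Restate the severity ranges as 0–24 (self-injury), 0–30 (aggressive/destructive) and 0–54 (total). Any severity of 1 to 3 recorded beside a frequency of never should be queried with the site before the rule is applied, not silently overwritten. A zero for an absent problem is consistent with how SAP 8.1.2.10 scores the ABC-2.

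The cost is two sentences, three ranges, one check and the matching scoring code. No new data are needed, because the frequency rating that drives the zero is already collected for every item. The unit of the three-item limit in SAP 4.2.3 remains open for severities that are truly missing and should be stated there.

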8.1.2.12. Child Sleep Habits Questionnaire (CSHQ)

The Child Sleep Habits Questionnaire (CSHQ) will be completed at all Screening and Baseline visits (Visits 1, 2, 3), as well as Week 6 (Visit 9), End of Treatment (Week 13, Visit 16), and Follow-up (Visit 17). Each item is scored on a 3-point scale, where 1=rarely; 2=sometimes; 3=usually. Items 32 and 33 are scored as 1 = not sleepy, 2 = very sleepy and 3 = Falls asleep A higher score reflects more disturbed sleep behavior. The items are grouped into 4 domains and 8 subscale scores are derived from the 33 items in these 4 domains. The subscale scores are a sum of the items within that subscale, except for a few items which are reversed for scoring. Missing items will be imputed as defined in section 4.2.3. The subscale scores will only be calculated if all items in subscale are answered or can be imputed. The subscales and their corresponding items are listed below.

- 1. Bedtime Resistance: Items 1, 3, 4, 5, 6, 8, where items 1 and 3 are reversed. Subscale score ranges from 6-18.
- 2. Sleep Onset Delay Behavior: Item 2 where item 2 is reversed. Subscale score ranges from 1-3.
- 3. Sleep Duration: Items 9, 10, 11, where items 10 and 11 are reversed. Subscale score ranges from 3-9.
- 4. Sleep Anxiety: Items 5, 7, 8, 21. Subscale score ranges from 4 12.
- 5. Night Wakings: Items 16, 24, 25. Subcale score ranges from 3-9.
- 6. Parasomnias: Items 12, 13, 14, 15, 17, 22, 23. Subscale score ranges from 7-21.
- 7. Sleep Disordered Breathing: Items 18, 19, 20. Subscale score ranges from 3-9.

8. Daytime Sleepiness: Items 26, 27, 28, 29, 30, 31, 32, 33, where item 26 is reversed. Domain score ranges from 8 – 24.

The total score will be calculated as a sum of all 33 items, with items 1-3, 10-11, and 26 reversed. The total score will range from 33-99 and will only be calculated if all items are answered. Within-subject change is the difference between the score at each timepoint and the score at Baseline (Visit 3).

Summary statistics for the derived scores and their changes from baseline in the total sleep disturbance score and domain-specific CSHQ scores will be displayed at all post-baseline visits. Test-retest reliability will be assessed for all scores collected during the Screening period (Visit 1, 2, and 3, pre-dosing) using Intraclass Correlation Coefficients (ICC). Changes from baseline will be analyzed using a Wilcoxon signed rank test. The total score will be presented in waterfall plots, histograms, and violin plots, and the subscale scores will be presented in a forest plot, as described in Section 8.1.2.

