11.4 Efficacy Analysis

Efficacy will be assessed by looking at within-subject changes from the Baseline period to EOT using the efficacy endpoints listed in Section 6.3.2.

The subject's baseline characteristics and symptom severity will be established based on assessments collected during the 4 to 6 week Screening/Baseline period. Baseline values will be based on the average values of visits 1, 2, and 3 for assessments collected at more than one visit. A Wilcoxon signed rank test will be used to test for improvement and an exact significance level will be computed.

Potentially influential factors will be considered and addressed with a linear regression model. This model may include covariates such as age, sex, nonverbal IQ (NVIQ) or NVIQ equivalent, genotype, history of regression (yes/no), ASD diagnosis (yes/no) with no more than two covariates included in any model. Descriptive statistics and corresponding graphics will be used to present the results. The safety and efficacy analysis details will be specified in the SAP.

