4.2.2. Baseline Values

Baseline values that are missing will not be imputed for safety or efficacy measures. For assessments collected at more than one visit during the Screening/Baseline period,the baseline measurement for an efficacy variable will be based on the average all non-missing values from visits 1-3.

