4.3. Definitions

- The baseline measurement for an efficacy variable will be based on the average values of visits 1-3 for assessments collected at more than one visit. For assessments collected once during the Screening/Baseline period, the most recent non-missing assessment will be used. For safety assessments, value at Visit 3 (Baseline) or the most recent non-missing assessment will be used.
- Age will be derived as the integer value of informed consent/assent date minus birth date plus one, then divided by 365.25.
- The age at time of assessment in calculated as (date of assessment date of birth + 1)/365.25.
- Body Mass Index (BMI) will be derived as weight in kilograms divided by height in meters squared.
- The change from baseline measurement for a variable at a particular visit will be derived as the measurement taken at the specified visit minus the baseline measurement. CGI-I will not have a change from baseline measurement; the within-subject treatment change is assessed by the value at the End of Treatment Visit.
- Treatment duration in days will be derived as follows: Date of Last Dose Date of First Dose + 1.
- Study duration will be defined as the total number of days in the study (date of last visit date of informed consent + 1).
- History of developmental regression will be determined from the medical history question as reported on the PMS diagnosis page of the CRF: "Has the child undergone a regression of skills in the past?" If coded as "yes" the subject is considered as having had a past developmental regression.
- Autism Spectrum Disorder (ASD) diagnosis will be derived from the PMS diagnosis page of the CRF. If ASD is checked to the under "confirmation of psychiatric co-morbidities", the subject is considered as having the disorder-
- Bipolar Disorder will be derived from the PMS diagnosis page on the Case Report Form (CRF). If "Bipolar disorders" is checked to the under "confirmation of psychiatric co-morbidities", the subject is considered as having the disorder.

- Attention Deficit Disorder will be derived from the PMS diagnosis page on the CRF. If "Attention Deficit Disorder" is checked to the under "confirmation of psychiatric co-morbidities", the subject is considered as having the disorder.

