8.1.2. Secondary Efficacy Analysis

The efficacy endpoints will be analyzed using a Wilcoxon signed rank test on the paired subject data from baseline to end of treatment (Visit 16) when applicable. Descriptive statistics will be used to summarize the data. For total scores, waterfall plots, histograms, and violin plots will also be created at the End of Treatment (EOT) visit with plots for all subjects and separate plots color-coded to indicate age group (9-12 years, 6-8 years, 3-5 years), NVIQ/DQ score (≥ 50 , < 50), sex (Male, Female) and number of concomitant medications (> 6, ≤ 6). The number of concomitant medications will be determined as defined in Section 4.3. For scales with domain scores, forest plots will be generated.

Results for each efficacy variable will also be listed by subject.

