8.1.2.10. Aberrant Behavior Checklist-2 (ABC-2)

The Aberrant Behavior Checklist-2 (ABC-2) will be completed at all Screening and Baseline visits (Visits 1, 2, 3), as well as Week 6 (Visit 9), End of Treatment (Week 13, Visit 16), and Follow-up (Visit 17). Each item is scored on a 4-point scale, where 0 = Not at all a problem; 1 = The behavior is a problem but slight in degree; 2 = The problem is moderately serious; 3 = The problem is severe in degree. The items are grouped into 5 subscales: Irritability (Subscale I, score ranges from 0 - 45), Social Withdrawal (Subscale II, score ranges from 0 - 48), Stereotypic Behavior (Subscale III, score ranges from 0 - 21), Hyperactivity/Noncompliance (Subscale IV, score ranges from 0 - 48), and Inappropriate Speech (Subscale V, score ranges from 0 - 12). The total score has a range from 0 - 174. Lower scores indicate fewer behavior issues. The subscale scores were calculated via a scoring algorithm in the EDC. These calculated scores will be used for the analysis. Missing items will be imputed as defined in section 4.2.3. Subscale or total scores may be calculated from answered and imputed items. If a total or subscale score is missing, then that subject will be excluded from the corresponding summaries.

Within subject change is the difference between the score at each measured timepoint and the score at Baseline (Visit 3). Summary statistics for the change from baseline in total and each subscale ABC-2 score will be displayed at all post-baseline visits. Change from baseline in the total and subscale scores will be analyzed using the Wilcoxon signed rank test. Test-retest reliability will be assessed for all scores collected during the Screening period (visits 1, 2, and 3, pre-dosing) using Intracass Correlation Coefficients (ICC). The total score will be presented in waterfall plots, histograms, and violin plots, and the subscale scores will be presented in a forest plot, as described in Section 8.1.2.

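### The SAP never estimates the change over the pre-dose visits and gives two conflicting efficacy baselines, one of which counts part of that change as on-treatment change

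*SAP*

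**What the plan says.** The schedule of assessments places Top 3 Concerns, ABC-2, CSHQ and GIHQ at Visits 1, 2 and 3, all before the first dose, and CGI-S at Visits 1 and 3. Protocol 9.1 puts Visit 2 two weeks after Visit 1 and Visit 3 a further two to four weeks later.

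The SAP gives these ratings two uses.

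- **Reliability.** For CSHQ, "Test-retest reliability will be assessed for all scores collected during the Screening period", by ICC. Sections 8.1.2.5, 8.1.2.9, 8.1.2.10 and 8.1.2.13 plan the same.
- **Baseline.** SAP 4.3 defines the efficacy baseline as "based on the average values of visits 1-3 for assessments collected at more than one visit". SAP 4.2.2 repeats this for non-missing values, and protocol 11.4 agrees: "Baseline values will be based on the average values of visits 1, 2, and 3".

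The scale sections then name a different baseline. For CSHQ (8.1.2.12): "Within-subject change is the difference between the score at each timepoint and the score at Baseline (Visit 3". For ABC-2 (8.1.2.10): "Within subject change is the difference between the score at each measured timepoint and the score at Baseline (Visit 3". GIHQ (8.1.2.13) and CGI-S (8.1.2.5 and 8.1.2.6) also use Visit 3. Top 3 Concerns (8.1.2.9) names no baseline visit.

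On testing, SAP 8.1.2 says: "The efficacy endpoints will be analyzed using a Wilcoxon signed rank test on the paired subject data", from baseline to Visit 16. Change summaries are planned for post-baseline visits only. The covariates in protocol 11.4 and SAP 7.2 are patient characteristics; neither list includes a run-in slope.

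**The concern.** With no control arm, repeated ratings before dosing are the most direct evidence on how these scores move without drug. Caregiver ratings can improve through repetition, expectation or regression to the mean. An ICC describes agreement; it does not report the direction or size of a mean shift. No planned output shows whether scores were already improving before the first dose.

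The baseline rule decides what happens to such an improvement. Under the average, part of it enters the tested change. Under Visit 3, that part drops out. Because both rules stand in the SAP, the tested quantity is undefined for CGI-S, ABC-2, CSHQ and GIHQ. The SAP's clause that it governs over the protocol cannot settle a conflict inside the SAP. Protocol 6.2.3 looks to these measures for preliminary signs of efficacy, and run-in drift could imitate those signs.

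**Working it through.** **1. The plan's own figure.** SAP 4.1 gives power 0.80, 0.85 and 0.90 at effect sizes 0.68, 0.73 and 0.79 (n=20, two-sided 0.05, signed-rank). A one-sample noncentral t with n multiplied by 3/π gives 0.803, 0.855 and 0.904. Simulating the exact signed-rank test (critical value 52, true level 0.048) gives 0.804, 0.855 and 0.903. The plan's figures reproduce, and the same simulated test is used below.

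**2. Share of run-in change carried into the averaged baseline.** Lower is better on all these scales. Let D be the Visit 1 to Visit 3 improvement and f the fraction of it that occurs by Visit 2. Then V1 = V3 + D and V2 = V3 + (1 − f)D, so

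(V1 + V2 + V3)/3 = V3 + D(2 − f)/3.

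- All drift before Visit 2 (f = 1): share 1/3.
- All drift after Visit 2 (f = 0): share 2/3.
- Linear, 4-week run-in (f = 2/4): share 1/2.
- Linear, 6-week run-in (f = 2/6): share 5/9, or 56%.

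For CGI-S, if the average applied, (V1 + V3)/2 = V3 + D/2, a share of 1/2. With a Visit 3 baseline the share is zero.

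**3. Illustrative effect on the test.** The documents give no drift or ICC, so these are assumptions: normal scores, one-visit SD 1, ICC 0.7 to 0.9, no drug effect, n=20, drift stopping at Visit 3. Error variance of the change is (1 − ICC)(1 + 1/3) with the average and 2(1 − ICC) with Visit 3. For D = 0.3 and share 1/2, the shift in SDs of the change is 0.15/√(4/3 × 0.3) = 0.24 at ICC 0.7, 0.15/√(4/3 × 0.2) = 0.29 at 0.8, and 0.15/√(4/3 × 0.1) = 0.41 at 0.9. Simulated two-sided rejection rates with the averaged baseline (share 1/2):

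| D (one-visit SD) | ICC 0.7 | ICC 0.8 | ICC 0.9 |
|---|---|---|---|
| 0.2 | 0.098 | 0.126 | 0.201 |
| 0.3 | 0.165 | 0.223 | 0.398 |
| 0.5 | 0.370 | 0.518 | 0.808 |

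With a Visit 3 baseline the rate is 0.046 to 0.049 throughout. At D = 0.3, a share of 1/3 gives 0.098, 0.123 and 0.203; a share of 2/3 gives 0.257, 0.357 and 0.620.

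**4. Drift that continues on treatment.** With a 4-week run-in the three visits have a mean time of −2 weeks, so the average credits 13 + 2 = 15 weeks of drift and Visit 3 credits 13. With a 6-week run-in the average credits 13 + 10/3 = 16.3 weeks. At 0.1 SD per 4 weeks (4-week run-in), rejection at ICC 0.7, 0.8 and 0.9 is 0.407, 0.563 and 0.854 from Visit 3, and 0.685, 0.852 and 0.989 from the average. Changing the baseline alone does not solve this.

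**5. A direct within-child contrast.** (Visit 16 − Visit 3) − (13/4)(Visit 3 − Visit 1) removes linear drift for a 4-week run-in; simulated rejection is 0.047 to 0.051. With independent visit errors its variance is 1 + 4.25² + 3.25² = 29.6 units of one-visit error variance, against 2 for Visit 16 − Visit 3. For a 6-week run-in (multiplier 13/6) it is 1 + 3.17² + 2.17² = 15.7 units.

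**The case against.** Much of the case on the other side stands.

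- A reader might infer that the three pre-dose ratings serve only the ICC. They do not: 4.2.2, 4.3 and protocol 11.4 also make them the baseline.
- A reader might infer that run-in drift is built into the tested change on every scale. The scale-specific text says Visit 3 for CGI-S, ABC-2, CSHQ and GIHQ. Only for Top 3 Concerns does the average apply without contradiction.
- The run-in is not the only internal comparison. Top 3 Concerns, ABC-2, CSHQ, GIHQ and CGI-S are rated again at Visit 17, about two weeks after treatment ends. That comparison is imperfect, but it is planned.
- Regression to the mean should not be pressed hard. The only rating-scale entry threshold is CGI-S of 3 or more. Top 3 Concerns is more exposed than the others, because caregivers choose the concerns for being troublesome.
- Averaging has a real benefit: error variance 4/3 against 2 units.
- The ICC is purposeful, since protocol 6.2.3 includes learning how the measures perform, and by-subject listings will show the run-in values.
- A contrast of Visit 3 to Week 6 against Visit 1 to Visit 3 would be a poor remedy. The titration table starts 12 mg/kg BID in Week 7, so it stops before that dose. Unscaled, it compares 6 weeks with 4 to 6. Its error variance (Week 6 − 2 × Visit 3 + Visit 1) is 1 + 4 + 1 = 6 units against 2.

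None of this supplies an estimate of the pre-dose change or reconciles the two baseline rules.

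**Conclusion.** The point holds in a limited form. No planned analysis estimates the Visit 1 to Visit 3 change, and the SAP has two incompatible efficacy baselines. Where the three-visit average is used, one third to two thirds of a steady-direction run-in improvement is counted as on-treatment change. This is settled only for Top 3 Concerns and depends on which rule governs elsewhere. Using Visit 3 removes that carry-in but not drift that continues.

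The rejection rates illustrate sensitivity to assumed drift and ICC; they do not predict this trial's error rate, and the documents do not show that drift will occur. A reader might go further and conclude that any efficacy signal would be an artefact of the baseline. The documents do not support that.

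Severity is modest: there is no primary efficacy variable, the design is exploratory and SAP 7.5 makes all p-values nominal. The sample size is unaffected, since it rests on CGI-I, which has no pre-dose value.

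**What to change.** 1. State one efficacy baseline rule and use it consistently in 4.2.2, 4.3 and all of 8.1.2, including 8.1.2.9, where no visit is named.
2. For Top 3 Concerns, ABC-2, CSHQ, GIHQ and CGI-S, report the Visit 1 to Visit 3 change (estimate, interval, signed-rank) beside the Visit 3 to EOT change, with the length of each interval.
3. Show the EOT change from the other baseline as a sensitivity analysis. The average is more precise and Visit 3 avoids the carry-in, so both are worth seeing.
4. Label any formal within-child contrast of run-in and on-treatment change as exploratory, scale it for each child's interval lengths, run it to EOT rather than Week 6, and state its loss of precision. A null result from it would say little at n=20.

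The cost is one extra table per scale, from data already collected. There is no new visit, no added burden on families and no change to the sample size.
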